- a. **Recruitment, sample description and inclusion/exclusion criteria.** Participants will be recruited through advertisements on social media, paper flyering, advertising on local list-servs, and by peer recruitment. Our lab has successfully attracted over 340 participants to complete our screening measures using these methods in the past year. Interested individuals can contact the laboratory via email or phone call to arrange a phone screen, where we will assess likely eligibility for the study.
 - i. **Inclusion criteria:** A) Between 18 and 35 years of age,
 - ii. **Exclusion criteria:** A) AUDIT Score less than or equal to 14, B) Non-drinker C) positive result on urine drug screen or breathalyzer at the start of any study visit, D) inability to complete MRI (e.g. presence of ferromagnetic objects in body), E) current use of medications that alter the hemodynamic response, such as insulin, F) history of trauma resulting in loss of consciousness longer than 15 minutes, G) for females, pregnancy, H) current (within the last 3 months) use of opioids to avoid acute precipitated withdrawal due to opioid receptor antagonism I) treatment for a DSM5 disorder other than anxiety or depression through therapy J) treatment for a DSM5 disorder through medications, K) greater than 10 uses of illicit substances in the last year.
- b. **Feasibility:** We have recruited 45 participants to our laboratory's studies in the past year and conducted 45 MRI scans. To recruit ~10 participants in one year, we need to recruit 1 participant per month and conduct 2 scans per month. This is well within the capacity of our laboratory operations.

C. Study Design and Research Methods. After completing an informed consent procedure, participants will sign a consent form. They will then complete a psychiatric interview and receive 5 capsules. Participants will return five days later for visit 2. On visit 2, they will complete a medication side-effect questionnaire. If they report side effects that are more

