Vulnerable populations are routinely excluded from experimental studies with more than minimal risk and without an established therapeutic benefit.

b. Risks/Discomforts and Benefits Ratio

Benefits: Participation in this study will not provide any known direct benefit.

Participants will receive psychiatric assessment and will be notified if anything pertinent to their health is discovered. The primary benefit of this study will be to others. The knowledge gained from this study could help develop treatments and provide information about who those treatments will work best on.

Risks and risk management: Known risks and discomforts associated with study procedures and steps to mitigate or minimize the risks are described below.

MRI: There are no known long-term risks of MRI scans. However, people are at risk for injury from the MRI magnet if they have certain metal objects in their bodies. These include implanted electrical devices such as pacemakers, cochlear implants, delivery pumps or brain stimulators. People with implanted metal such as aneurysm clips (metal clips on the wall of a large artery), permanent eyeliner, shrapnel fragments or some dental implants and prostheses (including metal pins and rods, heart valves) are also at risk. Welders and metal workers are also at risk for injury because of possible small metal fragments in the eye. Individuals with back problems may have back pain or discomfort from lying in the scanner. Individuals with fear of confined spaces may become anxious during an MRI. The noise of the MRI machine can be loud enough to damage one's hearing, especially in people who already have hearing loss.

1. To minimize risk from metal objects, participants will be screened for metal in their body using the MRI safety screening questionnaire, and individuals who report metal in their bodies will be excluded from the study.
2. Volunteers who are pregnant or planning to become pregnant during the study cannot participate. For female participants, a urine pregnancy test will be given no more than 24 hours before each MRI session. If a pregnancy test is positive or uncertain, she may not be in the study.
3. Participants will be able to communicate with MRI technologist during the scan and can ask to be removed from the scanner at any time if they become anxious or feel uncomfortable during the scan.
4. The participant will be fitted with earplugs and headphones to muffle the sound.

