c. Confidentiality: Medical records will be handled to prevent breach of privacy at a level considered sufficient for sensitive health care data. Confidentiality and information technology standards will be placed to protect electronic repositories of patient data as well as other clinical patient related materials. Research data not managed electronically will be stored using codes. No personal identifiers will be used. Data will be kept in password-protected computers, either located in access-controlled areas (servers), or, if transferred onto individual workstations, on encrypted media that protect privacy even if storage media are subject to theft. Samples will be kept in locked storage in access-controlled areas. Full access to data will be provided, under conditions of confidentiality, to individuals or groups

conducting quality assurance and appropriate regulatory agencies. With these exceptions, only study investigators and their staff will have access to the samples and data. When reporting the results of this research in medical journals or at scientific meetings, the people who take part will not be named and identified. We will not release any information about subject research involvement without the subject's written permission. The Federal Privacy Act protects the confidentiality of medical records. However, the Act allows release of some information from a subject's medical record without the subject's permission; for example, if it is required by the FDA, members of Congress, law enforcement officials, or other authorized people.

d. Naltrexone:

i. Common and Serious Side Effects of Naltrexone

Nausea, sleepiness, headache, dizziness, vomiting, decreased appetite, painful joints, muscle cramps, cold symptoms, trouble sleeping, toothache.

ii. Serious side effects of naltrexone may include:

Risk of opioid overdose. Accidental overdose can happen in two ways. Naltrexone blocks the effects of opioids, such as heroin or opioid pain medicines. Patients who try to overcome this blocking effect by taking large amounts of opioids may experience serious injury, coma, or death. After receiving a dose of naltrexone, the blocking effect slowly decreases and completely goes away over time. Patients who are taking naltrexone for an OUD can become more sensitive to the effects of opioids at the dose used before, or even lower amounts. Using opioids while on naltrexone can lead to overdose and death.

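### The exclusions look back at opioid use but do not ask about an expected opioid need in a capsule week, although the protocol says naltrexone blocks opioid pain relief

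*Combined protocol and SAP*

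**What the plan says.** Three exclusions in Section IV.B.a.ii bear on opioids or drug use:

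- H excludes "current (within the last 3 months) use of opioids to avoid acute precipitated withdrawal due to opioid receptor antagonism".
- C excludes a "positive result on urine drug screen or breathalyzer at the start of any study visit".
- K excludes "greater than 10 uses of illicit substances in the last year".

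Section IV.D.d.ii, on serious side effects, states "Naltrexone blocks the effects of opioids, such as heroin or opioid pain medicines" and closes its overdose paragraph with "Using opioids while on naltrexone can lead to overdose and death". On offset it says "After receiving a dose of naltrexone, the blocking effect slowly decreases and completely goes away over time", and gives no duration.

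The risk-minimisation text (Section IV.D.d.iii) lists video monitoring of adherence, two days at 25 mg before the full dose, and a side-effect questionnaire with care for moderate or severe effects.

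Under Section IV.C, participants receive 5 capsules at visit 1. At visit 2 they are tested for alcohol and drugs and scanned, then go home with 5 more. Section IV.C.a makes dosing double-blind and counterbalanced, with allocation revealed after the study ends.

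**The concern.** The protocol names a specific interaction between the study drug and opioid pain medicines. Its opioid exclusion, however, is written for a different hazard, precipitated withdrawal in someone who has recently used opioids. Someone who has not used opioids but knows that they will need them passes that test.

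At stake is the safety and comfort of a volunteer who, by Section IV.D.b, gains no known direct benefit. If a scheduled procedure falls in the naltrexone week, opioid pain relief may not work. The treating clinician may not know why, because the participant does not know which capsules they hold. The supplied text describes no unblinding before study completion.

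**Working it through.** No figure in the plan needs reproducing. The check is whether any written provision catches a defined test case.

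**Test case.** An otherwise eligible drinker aged 25, with no opioid use in the last 3 months, a negative drug screen and no illicit use, has a procedure with opioid pain relief booked for a capsule week.

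| Provision | What triggers it | Catches the test case before capsules are given? |
|---|---|---|
| Inclusion A | Age 18 to 35 | No |
| Exclusion H | Opioid use in the last 3 months | No: looks back only |
| Exclusion C | Positive test at a visit | No: nothing yet to detect |
| Exclusion K | Count of illicit uses in the past year | No: past and illicit only |
| Exclusion E | Current medicines altering the hemodynamic response | No: not about expected pain relief |
| Exclusion J | "treatment for a DSM5 disorder through medications" | No: psychiatric treatment only |
| Exclusions A, B, D, F, G, I | Drinking, MRI safety, head trauma, pregnancy, treatment for other disorders | No |
| Risk minimisation (IV.D.d.iii) | Adherence, dose ramp, side effects | No: no opioid question |

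**What criterion C does over time.** The visit 2 test comes after the first 5 capsules and before the second 5.

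- Placebo first: opioid use detected at visit 2 would stop the participant before any naltrexone. This is real protection.
- Naltrexone first: any use in week 1 has already coincided with naltrexone when the test is done.
- Either order: use during the second capsule period can be found only at the last visit.

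So C partly gates the second period, but it does not prevent exposure within either week. The test panel is not stated, so whether a prescribed analgesic would be detected is unknown.

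**Period to cover.**

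- Capsule days after visit 1: 5 + 5 = 10, of which 5 are naltrexone. Because dosing is blinded, a screening question has to cover both weeks.
- Participants whose naltrexone falls in the second period: half of about 10, so 10 / 2 = about 5. For them the block is still wearing off after the last capsule, and Section IV.D.d.ii does not say for how long.

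These figures set the window for the question. They do not measure the risk.

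**The case against.** **Rarity.** The case needs an adult aged 18 to 35, with no opioid use for 3 months, whose need falls within two 5-day periods, in a sample of about 10. This stands. It limits the weight of the point but does not close the gap, because the remedy is so cheap.

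**Unseen material.** Consent precedes capsule release and a phone screen precedes both. The consent pages were removed and the screening form is not shown, so either may warn or ask about opioids. A reader might infer that such a volunteer would certainly be dosed. The documents do not support that; they show only that no written criterion stops it.

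**Overdose.** A reader might also infer that a planned procedure exposes the participant to the fatal overdose in the warning. Section IV.D.d.ii explains two routes: taking large amounts to overcome the block, and heightened sensitivity in patients treated for opioid use disorder. Neither describes supervised pain relief in a healthy volunteer. Only the general closing sentence reaches that far, so the point should rest on blocked pain relief.

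**Pregnancy wording.** Section IV.D.b says "Volunteers who are pregnant or planning to become pregnant during the study cannot participate". This appears under MRI risks and is not an inconsistency in how naltrexone is handled. It shows only that the protocol already uses forward-looking eligibility wording.

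**Conclusion.** The omission is real and narrow. As written, neither the exclusions nor the risk-minimisation text screens for an expected opioid need, although the protocol states the interaction that makes one relevant. The supported harm is ineffective opioid pain relief under double-blind dosing, in a volunteer with no known direct benefit. Criterion C reduces but does not remove the exposure.

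The frequency cannot be estimated from the documents and is probably very small. The conclusion assumes that the written criteria govern who receives capsules; a screening question or consent warning not shown here could already deal with it in practice. The point concerns participant safety only and leaves the estimand, the paired analysis and the interpretation unchanged.

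A reader might extend the argument to exclusions for known liver disease or a past reaction to naltrexone. The documents list liver damage and allergic reactions as possible effects of treatment. They do not say that pre-existing disease or a past reaction raises the risk here, so those exclusions would rest on outside clinical judgement and are not part of this point.

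**What to change.** Extend criterion H with: *or expected need for opioid medication (e.g., a planned procedure) during either capsule week or for a period after the last capsule set by the study physician*. Ask this by self-report at the phone screen or at visit 1, before capsules are released. The study physician needs to set the tail because the protocol gives no duration for the block.

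The cost is one amendment and one question on the existing screen, with no laboratory test, extra visit or change to the analysis. The downside is possibly one screen failure, or a participant rescheduled until after the procedure.

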COMIRB Protocol

COLORADO MULTIPLE INSTITUTIONAL REVIEW BOARD
[name] [contact] [contact]

Protocol #: 21-2886

Project Title: Opioid Modulation and Neural Reward Activation in Healthy Adults

Principal Investigator: [name]

Version Date: 10/28/21

I. Hypotheses and Specific Aims:

1. Evaluate whether mu-opioid receptor blockade via naltrexone alters reward activation in the ventral striatum. In a study of 10 healthy, moderate drinking adults, we will use a crossover design to examine brain activation during a functional MRI scan during placebo and mu-opioid blockade.

Hypothesis 1. Relative to the placebo scan, participants will show reduced reward-related activation in the ventral striatum during the active medication scan.

2. Evaluate whether mu-opioid receptor blockade alters threat activation in the amygdala. In the same sample and design from Aim 1, we will use the Emotion Regulation Task to assess threat related activation in the amygdala during a functional MRI scan.

Hypothesis 2. Opioid receptor modulation will not affect threat related activation, consistent with naltrexone primarily targeting reward motivation.

3. Examine whether mu-opioid receptor blockade via naltrexone alters valuation of alcohol. In the same sample and study design from Aim 1, we will use the Alcohol Purchase Task to assess subjective value of an alcoholic beverage in order to link opioid-modulation directly to alcohol motivation.

Hypothesis 3. Relative to the placebo session, participants will be willing to pay less money for an alcoholic beverage during the active medication session.

This proposal aims to fill a gap in understanding how endogenous opioid function affects reward response in the brain. One of the leading hypotheses is that individuals who drink to maximize reward are more likely to benefit from naltrexone treatment, and the current proposal would provide evidence for this in a healthy sample. Further, this work could lead to a clinical study of reward-related brain activation and response to naltrexone treatment in adults with an Alcohol Use Disorder. This stands to improve precision medicine approaches to tailor treatments for alcohol use disorder.

II. Background and Significance:

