Neurotransmitter systems that interact with dopamine to encode reward are poorly understood. Animal studies show that mu-opioid antagonism blunts dopamine and ventral striatal activity (Walters et al. 2005). However, this has not been studied in humans. Psychopathology, such as substance use and mood disorders, are associated with altered nucleus accumbens activation to reward (Treadway and Zald 2013; Morales et al. 2018) and lower dopamine receptor concentration (Volkow et al. 1993). The treatment of such psychopathology is timely and important given the impact of the coronavirus (COVID-19) on increased incidence of depression (Salari et al. 2020) and substance use problems (Ahmed et al. 2020). Alcohol use remains one of the leading causes of death globally (Rehm et al. 2009), accounting for 88,000 annual deaths in the United States alone (Centers for Disease Control and Prevention 2004). The opioid system is involved in emotion (Nummenmaa and Tuominen 2018) and the mu-opioid receptor is involved in reward processing (Nummenmaa et al. 2018) but little is known about how this relates to psychopathology such as substance and alcohol use disorders.

This will be among the first investigations of how mu-opioid antagonism via naltrexone affects human monetary reward response. One previous study examined the effect of naltrexone on monetary reward response (Nestor et al. 2017), but this study used a monetary reward of less than \$1. Previous studies have shown that rewards of less than \$1 induce low levels of nucleus accumbens activation (Knutson et al. 2001). Further, the previous study administered only a single dose of naltrexone instead of using a steady-state during imaging (Nestor et al. 2017), so medication effects may have been absent for some participants. The study also used multiple study sites and scanners, which can increase variance. We will use a single site, a single scanner, a steady state of naltrexone during scanning, and a larger reward value of \$5 that has been shown to induce large activation levels in the nucleus accumbens (Figure 2).

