are presented with the image and are required to rate the experienced valence of that image using the same slider device. Subjects rate expected and experienced valence of 90 unique images: 30 erotic images, 30 non-erotic pleasant images (e.g., scenes of nature, cute animals), and 30 neutral images (e.g., forks, furniture). The same images are presented to each participant, but participants are randomly assigned to one of four random orders. The task takes place over 2 runs of approximately 8 minutes each. Prior to starting the task, participants are given instructions that included 3 practice cue/image pairs from each category to introduce them to the task and the relationship between each cue and image category. All images were publicly available and/or from affective picture sets currently used in research (Lang et al. 2005)(Marchewka et al. 2014)(Kurdi et al. 2017).

- c. The Structured Clinical Interview for the Diagnostic (SCID-5) and Statistical Manual for Mental Health Disorders 5, research version (First, Williams et al. 2015) will be administered to all participants by a psychiatrist or mental health professional (e.g. post-doc with clinical background). Diagnoses will be determined via a consensus meeting with the study psychiatrist, [name]. SCID-5 is a semi-structured interview guide for making diagnoses according to the diagnostic criteria published in the American Psychiatric Association's Diagnostic and Statistical Manual for Mental Disorders (DSM). With the release of the fifth edition (DSM-5), the SCID for DSM-5 (SCID-5) was published in 2013 and is the latest version available.
- d. We will administer questionnaires using Research Electronic Data Capture (REDCap), as the University of Colorado is part of the REDCap consortium (Patridge and Bardyn 2018). These metrics will establish history of substance use, psychopathology such as anxiety and depression levels, and trait levels of cognitive reappraisal.
 - i. **Adult Self Report:** (ASR) is used to obtain measures of internalizing and externalizing pathology (Rescorla and Achenbach 2004).

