Liver damage or hepatitis is possible. Patients should tell their practitioner about any of the following symptoms during treatment: stomach area pain lasting more than a few days, dark urine, yellowing of the whites of your eyes, tiredness, Practitioners may need to stop treatment using naltrexone if patients develop signs or symptoms of a serious liver problem, Depressed mood, Pneumonia, Serious allergic reactions, Skin rash, swelling of face, eyes, mouth, or tongue, trouble breathing or wheezing, chest pain, feeling dizzy or faint.

iii. Minimizing risk

Remote video monitoring will also be used to assess adherence. Dosing size will be set before participants receiving the naltrexone and participants will start on smaller doses (25mg) for two days before being raised to the final dosing to allow for adjustment to naltrexone and in case of adverse reaction to naltrexone. We will use a questionnaire to check for adverse reactions and will provide care as needed for moderate or severe side effects, such as nausea.

e. Psychological Tests

i. During the Standardized Clinical Interview for the DSM-V (SCID)
participants may discuss negative or traumatic events they have experienced. The SCID will be administered by a trained psychiatrist or by a member of the team trained by the team psychiatrist. Some of the questionnaires may cause emotional distress by asking about traumatic or unpleasant events from a person's life. While most individuals will tolerate this discomfort without problems, it is possible that the memories may trigger unhappiness. To mitigate the risk, study staff will allow participants to take breaks as needed. If serious distress arises, participants will be referred to a psychiatrist from the study team. This protocol may identify mental health problems, such as depression, suicidality, or substance use disorders. Problems with acute danger, such as suicidality will receive immediate attention and intervention. Individuals with diagnoses such as depression or alcohol use disorder will be given referrals for treatment.

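### Psychiatric eligibility turns on whether a disorder is being treated, and no rule uses the SCID-5 result, although the trial is described as one of healthy adults

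*Combined protocol and SAP*

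**What the plan says.** - **Intended population.** Section I: "In a study of 10 healthy, moderate drinking adults, we will use a crossover design". The title and the objective in section II also specify healthy adults. Section I says of its leading hypothesis about naltrexone that "the current proposal would provide evidence for this in a healthy sample".
- **Eligibility (IV.B).** The sole inclusion criterion is "Between 18 and 35 years of age". Exclusions I and J are "treatment for a DSM5 disorder other than anxiety or depression through therapy J) treatment for a DSM5 disorder through medications". None of exclusions A to K names a current psychiatric diagnosis.
- **Visit 1 (IV.C).** After consent: "They will then complete a psychiatric interview and receive 5 capsules". No eligibility decision is written between the two steps.
- **SCID-5 (IV.C.c).** It is given to all participants. "Diagnoses will be determined via a consensus meeting with the study psychiatrist". The meeting's timing relative to dispensing is not stated, and its result is not tied to eligibility.
- **If a disorder is found (IV.D.e).** "Individuals with diagnoses such as depression or alcohol use disorder will be given referrals for treatment". Acute danger is to be dealt with at once. Exclusion is not mentioned in either case.
- **Relevance to the outcome (II).** "Psychopathology, such as substance use and mood disorders, are associated with altered nucleus accumbens activation to reward".
- **Next study (IV.G).** Testing naltrexone in adults with alcohol use disorder is the goal after this pilot.

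**The concern.** Whether someone is being treated for a disorder is a different question from whether they have one. A volunteer with untreated depression or untreated alcohol use disorder passes both I and J. The protocol collects the information needed to identify such a person, through a structured interview with consensus diagnosis, and then gives that information no role in eligibility.

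What is at stake is the population to which the result applies. Nucleus accumbens activation to reward is the Aim 1 outcome, and the protocol itself links it to substance use and mood disorders. If some of about 10 participants have such disorders, the result cannot be presented without qualification as a finding in healthy adults. The separation from the planned study in alcohol use disorder is also blurred.

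**Working it through.** The plan states no figure on this point, so the main check is textual.

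**1. Two untreated volunteers, taken through the criteria as printed**

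| Criterion (IV.B) | Untreated depression | Untreated alcohol use disorder |
|---|---|---|
| Inclusion: age | no bearing | no bearing |
| A: AUDIT | not a measure of depression | as printed, admits only scores of 15 or more |
| C: drug screen, breathalyzer | sobriety at the visit only | sobriety at the visit only |
| I: therapy | not triggered | not triggered |
| J: medication | not triggered | not triggered |
| K: illicit substances | no bearing | limits illicit use, not alcohol |

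The other criteria (non-drinking, MRI safety, hemodynamic medication, head trauma, pregnancy, opioid use) do not address diagnosis.

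**2. Could AUDIT fill the gap?** As printed, criterion A excludes scores of 14 or less, so it selects the higher scorers. If the direction is a slip and 15 or more was meant to be excluded, scores of 8 to 14 still enter, and section IV.C.d regards 8 or more as hazardous or harmful use. Neither reading says anything about depression.

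**3. Does the protocol write an exclusion elsewhere when it wants one?** Yes. Section IV.D.b says that a woman whose pregnancy test is positive or uncertain may not take part. No such sentence accompanies the SCID-5.

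**4. Does the analysis handle it?** Section IV.F specifies paired t-tests of active medication against placebo. It has no covariate, subgroup or sensitivity analysis by diagnosis.

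**5. How likely is at least one case? (prevalence assumed)** Let p be the share of otherwise eligible volunteers with an untreated disorder. For 10 participants, the chance of at least one is 1 − (1 − p)^10. The number to interview in order to keep 10, on average, is 10 / (1 − p), rounded up.

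| p (assumed) | Chance of at least 1 in 10 | Interviews for 10 eligible |
|---|---|---|
| 5% | 1 − 0.95^10 = 40% | 10 / 0.95 → 11 |
| 10% | 1 − 0.90^10 = 65% | 10 / 0.90 → 12 |
| 20% | 1 − 0.80^10 = 89% | 10 / 0.80 → 13 |
| 30% | 1 − 0.70^10 = 97% | 10 / 0.70 → 15 |

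Each case is 1/10 = 10% of the sample.

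**6. Why the decision belongs before dispensing.** Section IV.F takes alpha 0.05 two-tailed, effect size 1.0 and 9 adults for 80% power. The exact paired t-test (noncentral t, N − 1 degrees of freedom, noncentrality 1.0 × √N) gives 74.8% at N = 9 and 80.3% at N = 10; the normal approximation needs 7.85, rounded up to 8. If affected participants were removed after enrolment without replacement, power would fall from 80.3% (10) to 74.8% (9), 68.1% (8) and 60.0% (7). Screening with replacement before dispensing avoids this loss.

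**The case against.** The best defence has four parts.

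- **The design is self-controlled.** Each person is scanned on both treatments, so a stable disorder does not confound naltrexone against placebo. This stands in full.
- **Some of the breadth looks deliberate.** Criterion I expressly tolerates therapy for anxiety or depression, and J has its own rationale in keeping other psychotropic drugs out of a drug-imaging study. This also stands. It means the sponsor did not require a disorder-free sample, and in that case the word healthy is what needs attention.
- **The sample can be described.** The SCID-5, BDI, ASR and CDDR allow participants to be characterised in the report. That helps the reader, but it does not make a mixed sample healthy, and no analysis by diagnosis is planned.
- **Staff may screen people out in practice.** The referral sentence sits in a paragraph on risk and is compatible with exclusion. That is possible, but a rule that is not written cannot be applied consistently or reported.

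A reader might go further than the text allows. One might infer that capsules are handed out regardless of the interview result, or that dispensing does not wait for the consensus meeting. The protocol says neither; it is silent on both. One might infer that a referral would start treatment between the scans and so trigger I or J mid-trial. Therapy for depression is exempt under I, and the scans are about 5 days apart, so this is speculative. One might infer that mixed diagnoses inflate the variance of drug response. Section II links disorders to activation, not to the response to naltrexone. Nor do the documents anticipate untreated psychosis among volunteers.

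**Conclusion.** The concern holds as a conflict between the stated population and the eligibility rules. Criteria I and J select on treatment received, nothing else in IV.B excludes a current diagnosis, and the role of the SCID-5 in eligibility is not stated. Followed as written, I and J leave untreated alcohol use disorder and depression eligible for a trial described as healthy adults.

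The damage is limited to interpretation: the healthy-sample conclusion and the boundary with the next study. The drug-placebo contrast remains valid for whoever is enrolled. The size depends on a prevalence that the documents do not give; over an assumed 5% to 30%, at least one case among 10 has a probability of 40% to 97%. That range assumes independent volunteers and no partial screening by AUDIT. The point should be settled before enrolment, because who was scanned cannot be changed afterwards.

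**What to change.** Reconcile sections I, II, IV.B, IV.C and IV.D.e in one amendment:

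1. Make eligibility depend on the SCID-5 consensus diagnosis, at minimum excluding a current alcohol or other substance use disorder.
2. For mood and anxiety disorders, choose one of two consistent positions: exclude current diagnoses and bring the therapy exemption in criterion I into line, or keep the exemption and stop describing the sample as healthy.
3. Require the consensus result to be recorded before the first capsules are released.
4. Resolve the direction of the AUDIT criterion at the same time. As printed only scores of 15 or more enter, and an alcohol use disorder exclusion on top of that could remove many entrants.

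No new procedure is needed, since the interview is already given. The cost is an amendment to the criteria and the visit 1 sequence, some more screen failures, and possibly a short wait between interview and dispensing. At the assumed prevalences, 11 to 15 interviews yield 10 eligible participants. Section IV.B reports over 340 people completing the laboratory's screening measures and 45 recruited to its studies in the past year. Those counts are for the laboratory's work generally, so they suggest feasibility without proving it for this population.
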